Dose dependent lens opacities have been observed after 1 month of dosing of 60 mg/kg in male Wistar rats (2 out of 30 rats), in 10 mg/kg dosed females (1 out of 20 rats), in 40 mg/kg dosed females (13 out of 19 rats) and in 60 mg/kg dosed females (26 out of 28 rats). Changes consisted of localized or diffuse (sub)capsular opacification at the posterior pole of the lens. The degree of opacification and the area involved was never so extended as to make visualization of the fundus difficult. This effect was not observed in dogs receiving chronic administration of R115777

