2.2 Pre-Treatment Evaluation (See Appendix 7)

Pre-treatment blood tests should be performed within 2 weeks prior to enrollment on the trial unless otherwise stated. The evaluation required prior to starting treatment phase "A" and "B" is listed in table form in Appendix 7.

2.2.1 History and Physical Examination: Complete history (including prior and concurrent therapy), physical examination including documentation of measurable disease, performance status, and signs and symptoms. A complete neurologic examination should be performed and focus on signs of sensory peripheral neuropathy. Height, weight and body surface area must be recorded. History and physical examination will be documented in case report forms as outlined Section 5.1.1. The BSA should be calculated from the average of 3 repeated measurements of weight and height on the same day using the formula below or a formula used at a participating institution:

$$BSA = \frac{Weight \ (kg)^{0.425} \bullet Height \ (cm)^{0.725}}{139.315}$$

2.2.2 Photography: When possible, plexiform neurofibromas that are visible on the body surface should be photographed prior to treatment with R115777 and placebo. A size marker should be taped to the skin in the field of view when appropriate, and

the plexiform neurofibroma should be photographed so that it fills the frame. Frontal and side images will be taken, as appropriate. Copies of photographs should be sent to the study coordinator, identified by the subject ID number, date, and treatment phase ("A" or "B") and treatment cycle number.

- 2.2.3 HEMATOLOGY: Complete blood counts, differential, platelet count, PT, PTT and fibrinogen.
- 2.2.4 CHEMISTRIES: Electrolytes (including calcium, phosphorus and magnesium), creatinine, SGPT, and bilirubin.
 - 2.2.5 URINALYSIS
 - 2.2.6 URINE PREGNANCY TEST: For all females of child-bearing potential.

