- 2.2.7 RADIOGRAPHIC EVALUATION (APPENDIX 1): MRI scan of the progressing plexiform neurofibroma(s) within 2 weeks prior to enrollment on study. In addition, if possible, MRI scan of all known additional, measurable plexiform neurofibroma(s) within 2 weeks of enrollment on study. The progressing plexiform neurofibroma(s) will be identified as index lesion(s), and will be studied by 3-D MRI. Should there be more than 3 progressing plexiform neurofibromas, the three most clinically relevant plexiform neurofibromas will be followed by 3-D MRI analysis. The imaging protocol outlined in Appendix 1 will be used each time MRI examinations are performed to assess the effect to R115777.
- 2.2.8 OPHTHALMOLOGIC EVALUATION: Ophthalmologic examination prior to or within the first three days of starting treatment with R115777 or placebo, including visual fields if the patient is able to cooperate with the exam and examination of the lens for opacifications.
- 2.2.9 TISSUE PROCUREMENT: In patients with easily accessible discrete neurofibromas or superficial plexiform neurofibromas, who consent to the procedure, biopsies will be performed prior to the first dose of treatment at study entry. In addition, attempts will be made to obtain tumor specimens from any patients requiring surgery for complications of their tumors or for unrelated medical problems. Peripheral blood mononuclear cells for FPTase assay (Section 2.2.10, Appendix 5) should be obtained at the same time as biopsy whenever possible. As this is an invasive procedure, patients may refuse biopsy and still be eligible for the study.

Kits will be supplied for handling and shipping of tumor specimens. To obtain a kit, please call [name] at [contact] seven days prior to the planned surgery (Appendix 3, Appendix 4). Two kits will be sent by FedEx to arrive several days prior to the surgical procedure. Included in the kits will be all media and tubes needed for shipment. Procedures for tissue handling and shipment are provided in Appendices 3 and 4, respectively.

2.2.10 FARNESYL-PROTEIN TRANSFERASE (FPTase) ACTIVITY IN PERIPHERAL BLOOD MONONUCLEAR CELLS (PBMC): Peripheral blood mononuclear cells (PBMC) will be

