3.4 ON STUDY EVALUATION (SEE APPENDIX 7)

- 3.4.1 HISTORY & PHYSICAL EXAMINATION: Every 2 weeks during the first 3 cycles on each treatment phase ("A", "B"). Physical exam should include assessment of performance status (documentation if changed from baseline), measurement of visible or palpable neurofibroma, height, weight and body surface area prior to every treatment cycle. A complete neurologic examination should be performed and focus on signs of sensory peripheral neuropathy. After cycle 3 perform prior to each cycle. History and physical examination will be documented in case report forms as outlined Section 5.1.1.
- 3.4.2 Photography: When possible, plexiform neurofibromas that are visible on the body surface should be photographed prior to treatment cycle 1, 4, 7, 10, and then after every 6 cycles on each treatment phase ("A", "B"). A size marker should be taped to the skin in the field of view when appropriate, and the plexiform neurofibroma will be photographed so that it fills the frame. Frontal and side images will be taken, as appropriate. Copies of photographs identified by the patient ID number, date, treatment phase ("A" or "B"), and treatment cycle should be sent to:

[name], R.N.
Pediatric Oncology Branch, NCI
[name]
[name]
Bethesda, MD 20892-1928

3.4.3 LABORATORY ASSESSMENT (see Appendix 7). Laboratory studies will be documented in case report forms as outlined Section 5.1.1.

Hematology: During the first 3 cycles of treatment on each treatment phase ("A", "B"), obtain complete blood count, differential and platelet count every other week (more frequent monitoring may be performed if the ANC <1,000/mm³ or platelet count <50,000/mm³). During subsequent cycles complete blood count, differential, and platelet count will be obtained prior to each cycle. PT, PTT and fibrinogen will be obtained prior to each treatment phase.

Chemistries: During the first 3 cycles of treatment on each treatment phase ("A", "B"), obtain electrolytes, creatinine, calcium, magnesium, phosphorus, SGPT, and bilirubin every other week. During subsequent cycles these tests should be performed prior to each treatment cycle.

Urinalysis: Prior to treatment cycle 1, 4, 7, 10, and then q 6 cycles on each treatment phase ("A", "B").

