3.4.4 RADIOGRAPHIC EVALUATION: Evaluate the index lesions by MRI prior to cycle 1 on treatment phase "A", and prior to cycle 4, 7, 10, and then after every 6 cycles on each treatment phase ("A", "B"). The protocol outlined in Appendix 1 will be used each

time MRI examinations are performed to assess progression or response to R115777 or placebo. In patients with clinical suspicion of disease progression MRI analysis should be performed earlier using the protocol outlined in Appendix 1. At the time of disease progression on treatment phase "A", if possible, a MRI scan of all known measurable plexiform neurofibromas in addition to the index lesions should be performed, in order to have a new baseline prior to treatment phase "B" (Appendix 1).

- 3.4.5 OPHTHALMOLOGIC EVALUATION: Prior to or within the first three days of starting treatment phase "A", and prior to or within the first 3 weeks of starting treatment phase "B". Exam should include visual fields if the patient is able to cooperate with the exam and examination of the lens for opacifications.
- 3.4.6 TISSUE PROCUREMENT: In patients with easily accessible discrete neurofibromas or superficial plexiform neurofibromas, who consent to the procedure, biopsies will be performed prior to the first dose of treatment on phase "A", and if feasible at one steady state time point on each treatment phase ("A", "B") (between day 15-21 on cycle #1) of treatment. In addition, attempts will be made to obtain tumor specimens from any patients requiring surgery for complications of their tumors or for unrelated medical problems. Peripheral blood mononuclear cells for FPTase assay (Section 3.4.7, appendix 5) should be obtained at the same time as biopsy whenever possible. As this is an invasive procedure, patients may refuse biopsy and still be eligible for the study.

Two kits will be supplied for handling and shipping of tumor specimens. To obtain the kits, please call [name] [contact]. Kits will be sent by FedEx to arrive several days prior to the surgical procedure. Included in the kits will be all media and tubes needed for shipment. Procedures for tissue handling and shipment are provided in Appendices 3 and 4, respectively.

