CARDIAC ARRHYTHMIA – Palpitations; Supraventricular and nodal arrhythmia - Atrial fibrillation; Supraventricular and nodal arrhythmia - Sinus tachycardia; Supraventricular and nodal arrhythmia - Supraventricular tachycardia; Ventricular arrhythmia - Ventricular tachycardia

CARDIAC GENERAL – Cardiopulmonary arrest, cause unknown (non-fatal); Left ventricular systolic dysfunction

COAGULATION – PTT (Partial Thromboplastin Time)

CONSTITUTIONAL SYMPTOMS – Rigors/chills; Sweating (diaphoresis); Weight loss **DERMATOLOGY/SKIN** – Dry skin; Hair loss/alopecia (scalp or body); Pruritus/itching **ENDOCRINE** – Hot flashes/flushes

GASTROINTESTINAL – Dry mouth/salivary gland (xerostomia); Flatulence; Gastrointestinal – Other (polydipsia); Ileus, GI (functional obstruction of bowel, i.e., neuroconstipation);

Obstruction, GI - Small bowel NOS; Taste alteration (dysgeusia)

HEMORRHAGE/BLEEDING – Hematoma; Hemorrhage, GI - Oral cavity; Hemorrhage, GI – Upper GI NOS

HEPATOBILIARY/PANCREAS - Liver dysfunction/failure (clinical)

INFECTION - Opportunistic infection associated with >= Grade 2 Lymphopenia

LYMPHATICS – Lymphatics - Other (localized lymphadenopathy)

METABOLIC/LABORATORY – Alkaline phosphatase; ALT, SGPT (serum glutamic pyruvic transaminase); AST,SGOT (serum glutamic oxaloacetic transaminase); Amylase; Calcium, serum-high (hypercalcemia); Glucose, serum-high (hyperglycemia); Magnesium, serum-low (hypomagnesemia); Potassium, serum-high (hyperkalemia); Sodium, serum-low (hyponatremia); Triglyceride, serum-high (hypertriglyceridemia)

MUSCULOSKELETAL/SOFT TISSUE – Muscle weakness, generalized or specific area (not due to neuropathy)

NEUROLOGY – Ataxia (incoordination); Extrapyramidal/involuntary movement/restlessness; Memory impairment; Mood alteration – Agitation; Mood alteration - Anxiety; Mood alteration - Depression; Neuropathy: motor; Psychosis (hallucinations/delusions); Seizure; Syncope (fainting); Tremor

OCULAR/VISUAL – Dry eye syndrome; Ocular/Visual - Other (abnormal vision)

PAIN - Pain - Back; Pain - Bladder; Pain - Bone; Pain - Joint; Pain - Muscle

PULMONARY/UPPER RESPIRATORY – Hiccoughs (hiccups, singulitus); Hypoxia;

Pneumonitis/pulmonary infiltrates; Voice changes/dysarthria (e.g., hoarseness, loss or alteration in voice, laryngitis)

RENAL/GENITOURINARY – Urine color change

VASCULAR – Phlebitis (including superficial thrombosis); Thrombosis/thrombus/embolism

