APPENDIX 7: REQUIRED STUDY EVALUATIONS

Prior To Starting Treatment, During, And Post Treatment for Each Study Phase ("A" and "B"):

Observation	Pretreatment (Phase A&B)	During Cycle (Phase A&B)	Prior to Each Cycle (Phase A&B)	Post Study
History & physical exam	X	q 2 weeks, Cycles 1-3	Χ	Χ
Performance status	X		X (document if changed)	X
Body surface area	X		X	
Photography of lesions, if	X		Cycles 4, 7, 10, then q 6 cycles	Χ
possible				
CBC, platelets, differential	X	q 2 weeks, Cycles 1-3	X	X
PT, PTT, Fibrinogen	X		X	Χ
Electrolytes and creatinine	X	q 2 weeks, Cycles 1-3	X	Χ
Ca ⁺² , Mg ⁺² , PO ₄	X	q 2 weeks, Cycles 1-3	X	Χ
SGPT, bilirubin	X	q 2 weeks, Cycles 1-3	X	Χ
Urinalysis	X		Cycles 4, 7, 10, then q 6 cycles	Χ
Urine pregnancy test	Females			
3D-MRI of index lesions	Phase A only		Cycles 4, 7, 10, then q 6 cycles	Χ
Ophthalmologic examination	X			Χ
QOL assessment	Phase A only		Cycles 4, 7, 10, then q 6 cycles	
Tumor Biopsy	Phase A only	Between days 15-21, Cycle 1 Phase A and B		
PBMC for FPTase	Phase A only	Between days 15-21, Cycle 1		

Nerve growth factor Phase A only

Cycles 4, 7, 10, then q 6 cycles

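### Section 3.4.5 lets the phase B eye examination follow a full 21-day dosing block, while Appendix 7 marks it as pretreatment, so a silent eye finding in a placebo-first patient examined late may not be attributable to placebo or R115777

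*Combined protocol and SAP*

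**What the plan says.** Section 3.4.5 sets two windows for the eye examination, which covers the lens and, if the patient can cooperate, the visual fields. For phase A it is done before dosing or in the first three days. For phase B it may be done "prior to or within the first 3 weeks of starting treatment phase 'B".

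Appendix 7 places the examination in the column "Pretreatment (Phase A&B". Its rows for 3D-MRI, quality of life, biopsy, PBMC and nerve growth factor are limited to phase A at pretreatment; the eye examination row is not. Section 2.2 gives the table its standing: "The evaluation required prior to starting treatment phase 'A' and 'B' is listed in table form in Appendix 7". Section 2.2.8 asks for "Ophthalmologic examination prior to or within the first three days of starting treatment with R115777 or placebo" and makes no separate allowance for phase B, though it may be meant for study entry only.

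Appendix 7 shows no eye examination during or before individual cycles. It marks one under Post Study. Section 3.7 ties post-study tests to the patient coming off study, and its own list (history and physical examination, photographs, laboratory tests, MRI) contains no eye examination. The heading of the Appendix 7 table, however, says that it covers the time after treatment for each of the two phases.

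**The concern.** In arm 2 the patient takes placebo in phase A and R115777 in phase B. An eye examination at the crossover should separate placebo time from drug time. If it is done at the end of the permitted window, the interval since the phase A examination contains the whole placebo phase, the washout and a full block of R115777. A change first seen then could have arisen in any of them. If the examination were also treated as the phase B baseline, a drug effect would be recorded as already present before drug.

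The lens check has a documented reason. Section 1.2.4 reports dose-dependent lens opacities in rats after 1 month of dosing, and adds that "The degree of opacification and the area involved was never so extended as to make visualization of the fundus difficult". A silent change is therefore plausible. There are also competing causes of eye findings in this population: Section 1.2.1 gives optic glioma in 15–20% of NF1 patients, and Section 2.1.1.2 names orbital lesions among the eligible tumours. Describing toxicity is a primary objective (1.1.3).

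**Working it through.** The plan states no figure on this point, so there is none to reproduce. The check compares the schedules and then works out exposure and intervals.

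**Exposure at the latest permitted phase B examination, placebo-first patient.** Dosing is every 12 hours for 21 days of a 28-day cycle (Section 3.1.3), so doses = days × 2.

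- Section 3.4.5: 21 × 2 = up to 42 doses.
- A three-day allowance, as in phase A: 3 × 2 = up to 6 doses.
- Appendix 7 read literally, or an examination in the washout: 0 doses.

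**Interval between the two examinations.** MRI is done before cycles 4, 7 and 10, then every 6 cycles (Section 3.1.4). The scan before cycle *k* falls on day (*k* − 1) × 28. Interval = scan day + 14 (washout, Section 3.1.1) + 21. Share on R115777 = 21 / interval. Months = days / 30.4375.

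| Progression called at scan before cycle | Scan day | Interval, days (months) | Share on R115777 |
|---|---|---|---|
| 4 | 84 | 119 (3.9) | 18% |
| 7 | 168 | 203 (6.7) | 10% |
| 10 | 252 | 287 (9.4) | 7% |
| 16 | 420 | 455 (14.9) | 5% |

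This assumes the phase A examination on the day of the first dose, progression called on the scan day, and a washout of exactly 14 days from then. The 119 days is not a floor, because Section 3.4.4 brings the MRI forward on clinical suspicion. With an examination in the washout, the share on R115777 is zero in every row.

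**Does another scheduled examination separate the phases?** Only if Post Study in Appendix 7 also means the end of phase A. The table heading allows that reading. The column label and Section 3.7 point to leaving the study, and crossover is not leaving the study. The documents do not settle it.

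**Who could be affected.** About 30 patients are planned for the placebo-first arm (Section 5.4.2). Of these, only patients who cross over, are examined late and have a new silent finding are concerned. The documents give no rate for the last two conditions, so the number cannot be estimated.

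**How likely a lens change is.** Rats at 1 month (Section 1.2.4): females 1/20 (5%) at 10 mg/kg, 13/19 (68%) at 40 mg/kg and 26/28 (93%) at 60 mg/kg; males 2/30 (7%) at 60 mg/kg. In dogs, "This effect was not observed in dogs receiving chronic administration of R115777". Nothing in the documents shows a lens change by day 21. Section 8.1.11, based on 2702 patients, names no lens event; its ocular entries, "Dry eye syndrome; Ocular/Visual - Other (abnormal vision", are listed with the relationship to drug undetermined.

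**The case against.** Section 3.4.5 sets the two windows in one sentence, which looks deliberate, and specific text would normally govern a summary table. Pretreatment is not strictly pre-dose in this protocol either: Section 2.2.8 sits under the pre-treatment heading and still allows three days of dosing. This stands. It makes the difference from Appendix 7 a matter for clarification rather than a proven error, and the zero-dose figure depends on reading the table literally.

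If Appendix 7 does require an eye examination at the end of phase A, the attribution problem largely disappears. That reading is open, and it is why the point is conditional.

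A reader might infer that a silent finding in a placebo-first patient can never be assigned to a phase. The documents do not support that. A late examination is permitted, not required. Every placebo-first patient also has an R115777-free examination at phase A entry, since prior R115777 is an exclusion (2.1.2.8). A reader might also infer that drug effects will be counted as baseline, but no section calls the phase B eye examination a baseline.

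Symptomatic changes would usually be dated by history and examination, scheduled "Every 2 weeks during the first 3 cycles on each treatment phase", and by adverse event recording (Section 7.3.1). Only silent findings are left. No analysis in Section 5.4.2 and no dose rule in Section 3.3 uses the date of this examination. These limits stand and set the size of the point.

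**Conclusion.** The point holds as a cheap improvement. The text permits a phase B eye examination after as many as 42 doses of R115777, the table marks it as pretreatment, and on the more natural reading of Section 3.7 nothing else scheduled divides the phases. In a placebo-first patient examined late in the window, a new silent finding may not be attributable to placebo or drug.

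This rests on two assumptions: that some sites use the late end of the window, and that Post Study does not apply at the end of phase A. The consequence is limited to descriptive toxicity attribution under objective 1.1.3, in an unknown and probably small number of patients. The rat signal makes the lens check worth doing well, but it does not show that human lens change within 21 days is likely. Time to progression, the sample size and the alpha are unaffected.

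**What to change.** - In Section 3.4.5, schedule the phase B eye examination in the 2-week washout, before the first phase B dose, with at most the three-day allowance used for phase A. Apply this in both arms, because the site is blinded.
- Align the Appendix 7 row with that window, and state whether Post Study applies at the end of phase A. If it does, say that one examination in the washout serves both purposes.
- Record any eye examination done after the first dose of a phase as on-treatment, not as baseline.

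Exposure to R115777 at this examination in a placebo-first patient falls from as many as 42 doses to 0, or to at most 6 if the three-day allowance is used. The change needs only text and table edits and moves an examination that is already required.

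The cost is a specialist appointment in a window of about 14 days, which weighs on families who travel far (Section 6.5). Part of that is offset by joining it to assessments already required before phase B: history and physical examination (Appendix 7) and coagulation tests (Section 3.4.3).

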3.5 CONCURRENT THERAPY

Other cancer chemotherapy, radiation therapy, immunotherapy, or investigational agents can not be administered to patients receiving R115777 or placebo.

Alternative Therapy: Oral vitamin or nutritional supplements may be used if approved by the patient's primary physician, and should be recorded in the patient's history and diary.

Pharmacokinetic data suggest that H₂ antagonists and proton pump inhibitors do not alter the exposure to R115777 to a clinically significant extent. Patients may use proton pump inhibitors or H₂ antagonists during the treatment portion of this study. However, patients should be instructed to use antacids (Mg- or Al-containing formulations) AT LEAST 2 hours before or after intake of the oral study drug.

3.6 OFF STUDY CRITERIA

3.6.1 ADMINISTRATIVE: A patient may be taken off the study for the following non-medical or administrative reasons:

- Patient refusal of further treatments (reasons must be noted on the patient's CRF).
- It is deemed in the best interest of the patient. In this instance the Principal Investigator should be notified and the reasons for withdrawal should be noted in the CRF.
- Serious protocol violation as determined by the PI or representative from CTEP.

3.6.2 TOXICITY: Recurrent grade 3 or 4 toxicity after dose reduction or persistent toxicity grade ≥2 for >10 days without administration of drug that is considered primarily related to study drug (Section 3.3). Persistent (>10 days) grade 2 toxicity should be discussed with the PI prior to removing the patient from the study. The protocol Principal Investigator and CTEP should be notified immediately in the event of severe or life-threatening toxicity ([name], [contact], [contact]

page operator, and CTEP, Investigational Drug Branch [contact] (recorder after hours).

If toxicity necessitates unblinding the study drug for a patient, the patient should be removed from the study.

- 3.6.3 Tumor Progression: Any patient with clinical or radiographic evidence of progressive disease (see Section 3.1.5) on treatment "phase A", as documented by 3D-MRI, following any treatment cycle will be switched to treatment "phase B" (from R115777 to placebo or vice versa). After disease progression on both treatment phases, patients will be removed from study (see Sections 3.1.5 and 5.2). The POB research nurse must be notified when the patient progresses after "phase A" (crossover notification to PMB) and when the patient progresses after "phase B" (i.e., off-study notification to Orkand and PMB) by faxing the completed Tumor Progression Checklist and the Crossover / Off-Study Form (Appendix 9A/B) to the Pediatric Oncology Branch (c/o [name]) at [contact].
- 3.6.4 The development of a concurrent serious medical condition that might preclude or contraindicate the further administration of R115777.

